patients in decision (measured using CPS) using multi-nominal regression model to adjust for observed covariates. Then we will examine if these associations vary across intervention and usual care control groups. We then will repeat the model with other independent variables (decision conflict and trust). Next, we will test the association denoted by path c (direct effect of DCS, CPS, and trust on outcomes). For continuous outcomes (HRQoL, AUA-SI, MAX-PC, CES-D, SWD, and PSQ-18), we will compute area under the curve (AUC) for each measure for each patient. We will analyze AUC summaries with univariate linear models. In our main analysis we will analyze the series of functional status measures using linear mixed models that predict the outcome from time, independent variables and their interaction. We will repeat the analyses described for path c, this time by including treatment received in the models. We will test if the observed effects of DCS, CPS or trust on outcomes will be weaker after controlling for treatment. These analyses will be performed within and between groups (intervention and usual care controls). Specific Aim 3: Hypothesis: Prostate cancer patients in the intervention group undergoing conjoint analysis-value clarification exhibit improved treatment choice, satisfaction with decision, lower regrets, and improved objective and subjective outcomes. Analysis for Specific Aim 3 uses intent-to-treat approach: all randomized participants will be included regardless of whether they drop out of the intervention or study. Analysis will involve comparison of the primary outcomes between intervention and usual care control groups. Improved treatment choice is operationalized as the likelihood of low-risk PCa patients receiving active surveillance than active treatment, and will be compared between intervention and usual care control group. To allow for different trajectories of the outcome measures and to afford flexibility in making contrasts within participants over time and across participants, while simultaneously controlling for potential confounders, we propose the participant-specific or mixed effects linear model, in which the mean outcome depends on fixed covariates and random effects. The primary fixed effects will be indicators for intervention group and hospital. We will also stratify the analysis by type of treatment. The random effects represent the unobserved factors that lead to variation of the individual participants outcome. Random intercepts for each participant permit modeling of natural variation across participants at baseline. In addition, random slopes or random effects for the trajectory of each participant over time, allow for variation of each participant about a mean, overall trajectory across all participants. Although less robust to model misspecification, the mixed effects paradigm offers special flexibility in longitudinal data when exposures vary over time and when dropout and missed visits lead to unbalanced groups. The target of inference is the participant-specific response to treatment over time. At each time point of interest, we will estimate from the fitted model the difference from baseline in outcome for the treatment and control groups and test the difference between these differences. Both univariate and multivariate results will be reported in terms of Wald test, point estimates, and 95% confidence intervals. Specific Aim 4: Hypothesis 4: Prostate cancer patients whose treatment is more concordant with their values markers will experience improved subjective and objective outcomes. This specific aim s for intervention group only. We will analyze the association of the concordance between stated individual preferences and actual treatment received with objective (PCa recurrence and complications), subjective (HRQoL, psychological wellbeing, SWD, and satisfaction with care) outcomes, across treatment groups, adjusting for covariates. Association between the value markers (profiles) and measures of outcomes and personal and clinical characteristics: The value markers will be studied for their relationship with socio-demographic and clinical characteristics. We will also assess the association of value markers with outcomes. We will perform logistic regression with outcomes as the dependent variable and dummy variables for the utility-based profiles obtained earlier as independent variables. We will perform this evaluation with and without adjusting for patient attributes in the logistic model. For each case (adjusting and not adjusting for patient attributes), the evaluation of association between these profiles and outcomes will be based on a likelihood ratio test of the set of odds ratios corresponding to the dummy variables of the profiles. Additionally, we will perform a sequence of pair wise tests of comparisons of the profiles in terms of the proportion of type of treatment received based on the Holms multiple comparisons approach. This procedure is hierarchical in that it will identify the utility-based profile at the start of the process before making other comparisons, thus protecting the Type I error from additional comparisons. Specifically, Holms approach tests each pair-wise comparison in ascending order of p-values. Successively larger p-values have less rigorous alpha. The sequential Holm tests terminate after the first non-significant comparison so no subsequent comparison is significance. Concordance and its assessment: Understanding and respect for the patients preference and values is the main aspect of concordance [69, 73]. Thus a first step in concordance involves the physician extracting and understanding the patients view, followed by an agreement between the physician and patient regarding a management plan that integrates their views. There exist many definitions of concordance. For the purpose of this study, we operationalized concordance as agreement between a patients value markers and the attributes (or characteristics) of the treatment that

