
the patient receives (choice). Association of concordance between stated preference and attributes of treatment received will be studied separately for each treatment using Kappa statistics. The degree of concordance then will be used as an independent variable to test its association with outcomes. For objective/clinical outcomes (i.e., complications and PCa recurrence), we will test the hypothesis that degree of concordance is associated with PCa recurrence (measured by PSA doubling time). To evaluate the effects of concordance on biochemical recurrence of PCa, we will analyze PSA levels on the log scale over time using a mixed model approach. We also will apply survival analyses (Kaplan-Meier, logrank and Cox model) to model effects concordance of treatment and covariates on time to PSA recurrence. For subjective outcomes of urologic symptoms (AUA-SI), generic and prostate specific HRQoL, psychological well-being (CES-D, MAX-PC), satisfaction with decision and satisfaction with care, we will perform inferential analysis with t, chi-squared and non-parametric tests. Wilcoxon matched-pairs test will be used for comparisons within concordance and non-concordance groups. A concordance group will be defined as at least 75% agreement between values markers and treatment related attributes. We will perform sensitivity analysis to test robustness of results. Primary analyses will compare baseline with six and 24 months assessments, as literature suggests these are the clinically most relevant time points. Secondary analyses will compare baseline with three month and one year outcomes. Proportion returning to baseline over time will be compared using chi-squared tests, using procedures such as Bonferroni, Scheffé, and step-down Holm corrections to adjust for multiple testing. We will use loglinear regression models with psychological well being, HRQoL and satisfaction with care scores (log) as dependent variables, logistic regression with return to baseline as the dependent variable, and degree of concordance as the independent variable. For repeated measures outcomes we will use linear mixed models (Proc Mixed).

The following documents are currently attached to this item:

There are no documents attached for this item.

Deception

Does your project use deception?

No

Data confidentiality

- x Paper-based records will be kept in a secure location and only be accessible to personnel involved in the study.**

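### Aim 4 does not say which analysis tests Hypothesis 4 for the subjective outcomes, and the within-group Wilcoxon tests it lists cannot do so

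*Combined protocol and SAP*

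**What the plan says.** The Analysis Plan, under Specific Aim 4, states the hypothesis as "Prostate cancer patients whose treatment is more concordant with their values markers will experience improved subjective and objective outcomes". It restricts the aim to one arm ("This specific aim s for intervention group only") and promises to analyse the association of concordance with "outcomes, across treatment groups, adjusting for covariates".

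Under the run-in heading on concordance and its assessment, the plan lists these analyses:

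- A graded exposure: "The degree of concordance then will be used as an independent variable to test its association with outcomes".
- For urologic symptoms, HRQoL, psychological well-being and satisfaction: "we will perform inferential analysis with t, chi-squared and non-parametric tests". The groups these tests compare are not stated.
- "Wilcoxon matched-pairs test will be used for comparisons within concordance and non-concordance groups".
- A cut-point: "A concordance group will be defined as at least 75% agreement between values markers and treatment related attributes".
- A label: "Primary analyses will compare baseline with six and 24 months assessments", with 3 and 12 months secondary.
- Chi-squared tests on the proportion returning to baseline, then loglinear and logistic regressions with degree of concordance as predictor, then linear mixed models whose exposure and time contrast are not given.

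For PSA outcomes the plan has a mixed model on log PSA, plus logrank and Cox models that include concordance.

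**The concern.** The hypothesis is a contrast between men with more and less concordance. Two Wilcoxon tests, one per group, each ask whether that group moved from baseline. Significance in one and not in the other is not evidence that the groups differ, because it can arise from unequal group sizes alone. Significance in both does not show that they are alike.

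Concordance is also not randomised. It depends on the treatment the man received, and the Background section reports that HRQoL differs by treatment. A t, chi-squared or Wilcoxon test cannot adjust for that.

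Finally, within-group, dichotomised and graded analyses stand side by side over many scales, with none named as the test of Hypothesis 4. The result that decides the aim could therefore be picked after the data are seen.

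**Working it through.** **The plan's own figures.** The Accrual section gives detectable differences of 1.2 points (whole trial) and 3.0 points (60 per arm) at 80% power and two-sided 0.05, with ICC 0.3, four follow-ups and 10% loss. The SD of a four-visit mean is SD × √((1 + 3 × 0.3)/4) = 0.689 × SD. At SD 8:

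- 324 per arm: 2.80 × 8 × 0.689 × √(2/324) = 1.21
- 54 per arm: 2.80 × 8 × 0.689 × √(2/54) = 2.97

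Both reproduce at the low end of the stated SD range (8 to 14). They concern the randomised arms. The documents give no figure for a concordant versus non-concordant contrast.

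**How often the two within-group tests disagree when the groups do not differ.** Inputs from the documents: 360 intervention men less 10% = 324; SD 8 or 14; correlation 0.3 (the stated ICC, used here as the baseline-to-visit correlation). Assumed, because the documents do not give them: 20%, 30% or 50% of men above 75% agreement, and a common true change of 3 or 5 points.

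The SD of change is SD × √(2 × (1 − 0.3)) = 1.183 × SD, which is 9.47 or 16.57. For a group of size n, z = change × √n / SD of change, and power ≈ Φ(z − 1.96). With powers p1 and p2, the chance that exactly one test is significant is p1(1 − p2) + p2(1 − p1).

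Example (SD 14, change 3, split 162:162): z = 3 × √162 / 16.57 = 2.30, power = Φ(0.345) = 0.635, so 2 × 0.635 × 0.365 = 46%.

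| SD | Change | Share above cut | Power, concordant / non-concordant | Exactly one significant |
|---|---|---|---|---|
| 14 | 3 | 50% | 0.635 / 0.635 | 46% |
| 14 | 3 | 30% | 0.431 / 0.779 | 54% |
| 14 | 3 | 20% | 0.308 / 0.830 | 63% |
| 14 | 5 | 50% | 0.970 / 0.970 | 6% |
| 14 | 5 | 30% | 0.845 / 0.995 | 16% |
| 14 | 5 | 20% | 0.681 / 0.998 | 32% |
| 8 | 3 | 50% | 0.981 / 0.981 | 4% |
| 8 | 3 | 30% | 0.878 / 0.998 | 12% |
| 8 | 3 | 20% | 0.723 / 0.999 | 28% |
| 8 | 5 | 20% to 50% | 0.989 or more in each | 0% to 1% |

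Simulating the Wilcoxon test itself (1,500 runs) gives slightly higher values at SD 14: 48%, 56% and 65% for a 3-point change, and 8%, 19% and 35% for 5 points. A direct between-group test on the same simulated data rejects in about 5%.

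The disagreement also has a direction when the concordant group is the smaller one. In the SD 14, 3-point, 20% row, the non-concordant test alone is significant in 0.830 × 0.692 = 57% of trials, and the concordant test alone in 0.308 × 0.170 = 5%. If the change is a decline after treatment, the 57% would look like support for Hypothesis 4.

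**Cost of the 75% split (illustration only).** For a normal score with a linear effect, a cut that leaves a share q on one side keeps φ(z_q)²/(q(1 − q)) of the information. At 50:50 this is 0.3989²/0.25 = 64%, and at 25:75 it is 0.3178²/0.1875 = 54%.

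**A direct contrast is feasible.** The detectable difference on the four-visit mean is 2.80 × SD × 0.689 × √(1/n1 + 1/n0). Over the same three shares this is 1.7 to 2.2 points at SD 8 and 3.0 to 3.8 points at SD 14.

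**The case against.** A reader might infer that Aim 4's primary answer rests on the within-group tests and that the graded measure goes unused. The documents do not support that. The same paragraph plans degree of concordance as the predictor in loglinear and logistic models, and the PSA models include concordance too. These test association between men. The t and chi-squared tests may well be between-group, since only the Wilcoxon sentence is marked as within. The word primary sits in a sentence justified by clinically relevant time points, and the next sentence makes 3 and 12 months secondary, so it can be read as ranking visits and not tests.

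Adjustment is not absent either. Aim 4 promises it, and the general methods add propensity-score and instrumental-variable work, with the propensity step done separately in the intervention group. Those methods model treatment received, not concordance, so they cover the problem only in part.

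The information-loss figures are also weakly tied to this trial. Agreement between latent profiles and the attributes of six treatments may take few values, its distribution is not given, and 75% agreement is not the 75th percentile. The loss arises only if the split replaces the graded models.

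The 324 can be disputed as well, because recruitment is already inflated to 800 for attrition. With 360 men the worked example becomes z = 3 × √180 / 16.57 = 2.43 and power 0.68, so 2 × 0.68 × 0.32 = 44% in place of 46%.

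What stands: the within-group test cannot test Hypothesis 4, and the plan does not say what does. By contrast, Aim 3 specifies a test of the difference in change between groups, and Aim 2 names a main mixed model with an interaction with time. Aim 4 has neither.

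**Conclusion.** The concern holds in limited form. For the subjective outcomes, Aim 4 lists a within-group test on a 75% split, simple tests with no stated contrast, and graded regressions, without naming the one that tests Hypothesis 4. If the within-group tests were used for that purpose, they would disagree under no true difference in about 4% to 65% of trials in most scenarios tried, and in 0% to 1% at SD 8 with a 5-point change. These figures rest on assumed shares above the cut, a common assumed change, normal scores and a correlation of 0.3. The 64% and 54% information figures are illustrative only. The simple tests cannot supply the promised covariate adjustment. This is worth correcting because a better analysis is largely in the plan already. It is not a finding that the aim cannot be answered.

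**What to change.** State that inference on Hypothesis 4 for the subjective scores rests on the planned linear mixed model in the intervention arm, with degree of concordance, time and their interaction. Read the concordance effect at 6 and 24 months, and adjust for baseline score, hospital and the variables in the section on potential confounders. Report it with and without treatment received, because treatment partly determines concordance and the two models answer different questions. Label the 75% split and the within-group Wilcoxon tests as descriptive or sensitivity analyses, and say which groups the t and chi-squared tests compare.

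The cost is SAP wording, with no new patients, visits or data. One decision is needed first: the plan names Kappa by treatment and a 75% rule but does not define a patient-level score for degree of concordance, so that score must be defined before outcome data are analysed.
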